7.3 Lost to Follow-up

A participant will be considered lost to follow-up if her or his parents or LARs cannot be contacted by the site or designee.

The following actions must be taken if the parents or LARs of the participants do not follow-up on the monthly electronic contact (until 6 months after dosing/randomization) or cannot be contacted by phone at the end of the study as planned in the SoA:

- For the monthly electronic contact: the electronic platform will send one reminder for 3 consecutive days. If there is no answer after the e-reminders, the site and/or designee will call the parents or LARs of the participant as soon as possible, discuss the importance of answering the follow-up questions with them, and ascertain whether or not they wish their infant to continue participating in the study.
 - It is to be noted that if both the electronic and phone reminders fail, the next monthly electronic contact (up until 6 months post-dosing/randomization) will take place. The participant will not be deemed lost to follow-up before the 12-months follow-up phone contact for France, Germany, and UK non-reconsented participants or the 24-months follow-up phone contact for UK reconsented participants takes place.
- For the 12 months follow-up phone contact for France, Germany, and UK non-reconsented participants or the 24 months follow-up phone contact for UK reconsented participants, and before a participant is deemed lost to follow-up, the investigator or designee must make every effort to regain contact with the parents or LARs of the participants (where possible, 3 telephone calls and, if necessary, a certified letter to the participant's last known mailing address or local equivalent methods). These contact attempts should be documented in the participant's medical record.
 - Should the parents or LARs continue to be unreachable, the participant will be considered lost to follow-up.

Discontinuation of specific sites or of the study as a whole are handled as part of Appendix 10.1.

8 Study Assessments and Procedures

- Study procedures and their timing are summarized in the SoA. Protocol waivers or exemptions are not allowed.
- Adherence to the study design requirements, including those specified in the SoA, is essential and required for study conduct.

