A participant will be regarded as having completed the study if the status recorded on the Subject Status Technical Form eCRF form is “Study Completed”. A participant will be considered as having discontinued the study if they have an eCRF status of study discontinuation. Otherwise, the participant will be considered as ongoing in the study. However, at the time of First Year Analysis:

- UK participants who declined reconsenting will be considered as having “Completed the Study”. Completion date will be the 12 Month Follow Up Call date.
- UK participants who completed 12 Month Follow Up Call but didn’t re consent yet will be considered as “Ongoing in the Study”
- UK participants who already re consented will be considered as “Ongoing in the Study”.

A listing of all participants with their treatment and study completion status, including the reasons for study discontinuation, will be presented for the All Randomized Set as well as:

- in participants who received Beyfortus as a routine medication (First Year Analysis only)
- in UK re consented participants (Second Year Analysis only)
- in UK re consented participants who received Beyfortus as a routine medication (Second Year Analysis only).

A listing of all screen failed participants with their details for screen failure will be presented for the All Screened Set. A separate listing of participants who failed at least one inclusion / exclusion criteria including a text description of the criterion failed will be presented for the All Screened Set.

A listing of all randomized participants with their randomization details, including immunization date and actual treatment received will be presented for the All Randomized Set as well as:

- in participants who received Beyfortus as a routine medication (First Year Analysis only)
- in UK re consented participants (Second Year Analysis only)
- in UK re consented participants who received Beyfortus as a routine medication (Second Year Analysis only).

A listing of all participants excluded from at least one analysis set will be presented for the All Randomized Set.

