6.6.2.2. Tipping-Point Analysis

Due to the open-label nature of the study, an excess of withdrawals might be observed in the no intervention group and be translated into a biased estimator when assuming the non-informative censoring hypothesis.

In order to test this hypothesis, a tipping point analysis^{8,9,10} will be performed to assess the impact of imputating missing data under a various range of hypotheses.

1. In order to perform the tipping point analysis, data will be imputed for all participants with missing data, (ie who discontinued the study, or with a RSV test equals to missing or Not Done) from both groups, several scenarios will be evaluated:
 - a. Best case scenario: no RSV LRTI hospitalization among the missing data in nirsevimab group whereas all missing data in the no intervention group will be imputed as RSV LRTI hospitalization.
 - b. Worst case scenario: all missing data in nirsevimab group will be imputed as RSV LRTI hospitalization whereas no missing data in the no intervention group will be imputed as RSV LRTI hospitalization.
 - c. The number of RSV LRTI hospitalizations imputed in each arm will be incremented from 0% (complete case analysis with no RSV LRTI hospitalization imputed in any arm), by 10%, to the total number of missing data in each arm. Remaining participants with missing data (from 90% of total number of missing data to 0%) will be then imputed as having no RSV LRTI hospitalizations.
2. For each combination:
 - a. Person-months will be imputed in both treatment groups using the overall distribution of person-months in the respective group for non-missing participants. The following values will be considered and evaluated as different scenarios: minimum value, Q1, Q2, Q3 and maximum value.
 - b. Corresponding Incidence Rates will be imputed in each treatment arm.
 - c. For non aggregated rows, Efficacy for participants with missing data will be provided

$$\text{Eff}_{\text{miss}} = 100 \times \left(1 - \frac{\text{Incidence Rate Miss Nirsevimab}}{\text{Incidence Rate Miss No Intervention}} \right) = 100 \times \left(1 - \frac{\text{IRN}_{\text{Miss}}}{\text{IRC}_{\text{Miss}}} \right)$$

- d. For non aggregated rows, Overall Efficacy will also be computed with its 2-sided 95% Confidence Interval (described by Breslow and Day as for primary analysis) and corresponding p-value

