$$\begin{aligned} \text{Eff}_{\text{Overall}} &= 100 \times \left(1 - \frac{\text{Incidence Rate Overall Nirsevimab}}{\text{Incidence Rate Overall No Intervention}} \right) = 100 \times \left(1 - \frac{\text{IRN}_{\text{Overall}}}{\text{IRC}_{\text{Overall}}} \right) \\ &= 100 \times \left(1 - \frac{\text{IRN}_{\text{Obs}} \times \text{Prop}_{\text{Obs}}^{\text{N}} + \text{IRN}_{\text{Miss}} \times \text{Prop}_{\text{Miss}}^{\text{N}}}{\text{IRC}_{\text{Obs}} \times \text{Prop}_{\text{Obs}}^{\text{C}} + \text{IRC}_{\text{Miss}} \times \text{Prop}_{\text{Miss}}^{\text{C}}} \right) \end{aligned}$$

With:

- ✓ IRN_{Obs} = Incidence Rate observed in nirsevimab group
 - ✓ IRC_{Obs} = Incidence Rate observed in No Intervention group
 - ✓ $Prop_{Obs}^N = \frac{NN}{NN+NN_{Miss}}$ = Proportion of observed person-time in nirsevimab group defined as
 - ✓ $Prop_{Obs}^C = \frac{NC}{NC+NC_{Miss}}$ = Proportion of observed person-time in No Intervention group defined as
 - ✓ $Prop_{Miss}^N = \frac{NN_{Miss}}{NN+NN_{Miss}}$ = Proportion of missing person-time in nirsevimab group defined as
 - ✓ $Prop_{Miss}^C = \frac{NC_{Miss}}{NC+NC_{Miss}}$ = Proportion of missing person-time in No Intervention group defined as
- e. Then, person-months imputed from these different scenarios in no intervention group (min, Q1, Q2, Q3, max) in step 2)a) will be aggregated by PROC MIANALYZE in SAS using Rubin's rule, for a same combination of percentages in step 1)c).
- f. Step 2)e) will be repeated 5 times for the same combination of percentages working on the person-months imputed in nirsevimab group (min, Q1, Q2, Q3, max).
- g. For a same combination of percentages in step 1)c), person-months imputed from the 25 different scenarios in both groups (min, Q1, Q2, Q3, max in nirsevimab group/ min, Q1, Q2, Q3, max in no intervention group) will be aggregated by PROC MIANALYZE in SAS.
- h. For each different aggregated row from steps 2)e), 2)f), 2)g), Overall Efficacy, corresponding 95% CI and p-value will be provided by PROC MIANALYZE in SAS.

In addition, a graphical representation of all efficacy results off complete aggregated rows (produced in step 2)g)) will also be provided.

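### The tipping-point analysis applies Rubin's rule to 5 or 25 fixed person-time scenarios, so its aggregated confidence intervals and p-values, which feed the only planned graph, are not valid

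*SAP*

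**What the plan says.** SAP 6.6.2.2 sets up the tipping-point analysis because withdrawals in an open-label trial may be informative.

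- **Who is missing (step 1).** Data are "imputed for all participants with missing data, (ie who discontinued the study, or with a RSV test equals to missing or Not Done".
- **Events (step 1c).** The share of missing infants counted as events rises from zero, "imputed in any arm), by 10%, to the total number of missing data in each arm".
- **Person-time (step 2a).** Values are imputed "using the overall distribution of person-months in the respective group for non-missing participants", at the minimum, three quartiles and maximum, each treated as its own scenario.
- **Unpooled rows (step 2d).** Each scenario keeps an exact CI and a p-value, by the primary-analysis method.
- **Pooled rows (steps 2e-2h).** The five control-arm values are combined first: "min, Q1, Q2, Q3, max) in step 2)a) will be aggregated by PROC MIANALYZE in SAS", and step 2e names Rubin's rule. This is repeated for each of the five nirsevimab values, and then all 25 combinations are pooled. For these rows, "Overall Efficacy, corresponding 95% CI and p-value will be provided by PROC MIANALYZE in SAS".
- **Graph.** The one planned figure is a "graphical representation of all efficacy results off complete aggregated rows", meaning the 25-scenario rows of step 2g.

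SAP 6.6.5.1.2 and 6.6.5.2.2 reuse the method for very severe RSV LRTI and for the country analyses. The SAP does not say on what scale, or with what standard error, estimates go into PROC MIANALYZE.

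**The concern.** Rubin's rule adds within-imputation variance to between-imputation variance. The between term estimates uncertainty about the missing values only if the completed data sets are random draws from a predictive distribution. Here they are five chosen points, equally weighted, with every missing infant in an arm given the same value at once. The between term therefore reflects which points were chosen. The imputed event count is also fixed within each percentage combination, so uncertainty about events does not enter at all.

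A tipping-point analysis exists to show which assumptions reverse the conclusion. A pooled row averages over scenarios that may lie on both sides of the boundary and reports one interval. A reader of the graph could take a row as safe, or as failed, when its scenarios disagree.

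**Working it through.** **The plan's own count.** Five values in each of two arms give 5 x 5 = 25 scenarios, as step 2g states.

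**Inputs from the SAP (2.3, 6.6.1).** There are 14,430 infants per arm, control incidence is 0.86% and efficacy is 60%. Control events are 14,430 x 0.0086 = 124, and nirsevimab events are 124 x 0.4 = 50. One day of follow-up is 1/30.4375 = 0.033 months.

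**Assumed, because the documents do not give them.** These are the missing rates, a mean follow-up of 2.5 months, a person-month grid of 0.033, 1.3, 2.5, 3.7 and 6.0, and pooling on the log rate ratio.

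**Formulas.** With eN and eC the total events per arm, W = 1/eN + 1/eC. B is the variance of the log rate ratio across M scenarios, and T = W + (1 + 1/M)B, with a t reference. Each scenario also gets its exact conditional-binomial interval.

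**3% missing, 10% imputed in nirsevimab only.**
- 3% of 14,430 is 433, and 10% of that is 43 events, giving 93 v 124.
- W = 1/93 + 1/124 = 0.01882, B = 0.00125, T = 0.01882 + 1.04 x 0.00125 = 0.0201.
- Mean log rate ratio = ln(93/124) = -0.288 and SE = 0.142. Pooled efficacy is 25.0% (1.0% to 43.2%), p = 0.043.
- The exact lower bounds run from -6.2% to +7.9%, and 10 of 25 are at or below 0.

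**10% missing, 10% imputed in both arms.**
- 1,443 missing and 144 events per arm give 194 v 268.
- W = 0.00889, B = 0.0135, T = 0.0230, so T/W = 2.6.
- The pooled CI is 2.0% to 46.5%, p = 0.037. The exact lower bounds run from -10.6% to +30.9%, and 3 of 25 are at or below 0.

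**The opposite direction.** Take 63 v 159 events (1.1% control incidence), 722 missing per arm (5%), 72 imputed in nirsevimab and none in control, and a grid of 0.033, 1.5, 3, 4.5 and 6 with mean 3. The pooled lower bound is -9.2%. The exact bounds run from -18.7% to +2.7%, with 3 of 25 above 0.

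**Low missingness.** On that second grid, with equal missing and equal imputed shares in both arms, T/W is at most 1.013 at 1% missing and about 1.08 at 2%, even with every missing infant counted as an event. The square root of 1.08 is 1.04, so the interval on the log scale is about 4% wider.

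**Dependence on the grid.** Return to 50 v 124 events with 10% missing and no events imputed. The pooled lower bound is 36.3% with 3 points per arm, 39.6% with 5 and 40.6% with 9. Listing each of the five values four times moves p from 1.5e-5 to 7.7e-6 with no new information.

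**Event steps.** At 63 v 159 with equal person-time, 62 extra nirsevimab events and none in control remove significance (exact two-sided p above 0.05). A first step of 10% reaches that count once 620 infants per arm are missing (620/14,430 = 4.3%). For one country (21 v 53, alpha 0.05/3) the count is 10, reached at 100 missing (100/4,810 = 2.1%).

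**Who counts as missing.** SAP 6.2 requires a recorded discontinuation: "Otherwise, the participant will be considered as ongoing in the study". Protocol 7.3 adds: "The participant will not be deemed lost to follow-up before the 12-months follow-up phone contact" for France, Germany and UK infants not reconsented, and sets the 24-month call for UK reconsented infants. The planned first participant (01 September 2022) reaches D366 about 01 September 2023, after the latest Primary Analysis date of 30 April 2023. On those two passages a silent infant is ongoing and is not imputed. Three passages point the other way. The Protocol 1.3 footnotes give non-response as an example of premature termination. SAP 5.1.3 allows a lost-to-follow-up date at the Primary Analysis. SAP 6.2 lists loss to follow-up as a discontinuation reason.

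**The case against.** The strongest reply is about weight. The confirmatory test is the exact interval of SAP 6.6.1, and no rule uses a pooled row. Step 2d already tabulates every scenario, so nothing is suppressed. The effect is negligible unless missingness is well above 1-2%, and the documents give no sign of how much there was. The pooled bound is not systematically flattering: in the 3% example it sits close to the median exact bound, and in the 10% example it is the more cautious of the two. Every pooled number also rests on a scale and standard error that the SAP leaves open. All of this stands, and it limits the point to minor or moderate. It does not make the aggregated inference valid.

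Three stronger readings are tempting, and the documents do not support them.

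- A reader might infer that silent infants escape the analysis altogether. The passages conflict, so this is not established. Medical-record collection (Protocol 8.1, SAP 5.2.1), site calls after failed reminders (Protocol 7.3) and contacts up to database lock (SAP 6.6.1) also reduce unseen events. The rerun at the First Year Analysis (SAP 6.6.7.10) falls after the 12-month call.
- A reader might infer that 10% steps cannot locate the tipping point. The counts above concern only the row with no control events imputed. Step 1c varies both arms, and the grid brackets the boundary, although coarsely.
- A reader might infer that the primary conclusion is at risk. At planned counts it takes 62 unseen nirsevimab events, with none in control, to overturn it.

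**Conclusion.** Steps 2e-2h are wrong as written: the aggregated 95% CIs and p-values have no valid interpretation, and the only planned graph is built from them. The same holds where 6.6.5.1.2 and 6.6.5.2.2 reuse the method. That conclusion does not depend on any assumed number.

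The size does. It rests on assumed missing rates, follow-up and grids (including a 0.033-month minimum), and on pooling the log rate ratio with variance 1/eN + 1/eC. On that basis a pooled row can fall on one side of zero while some of its scenarios fall on the other once about 3-10% are missing. The exact rows of step 2d remain valid and no decision depends on the pooled ones, so this is a minor-to-moderate point. The status of non-responding infants is a query, not a demonstrated error.

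**What to change.** 1. Remove the aggregated CIs and p-values (steps 2e-2h) from 6.6.2.2, 6.6.5.1.2 and 6.6.5.2.2.
2. Base the graph on the exact rows of step 2d, for example a grid of control by nirsevimab percentages marking which person-time scenarios have a lower bound above 0. For the country analyses, use the adjusted criterion of SAP 6.6.4.2.
3. Optionally, use finer event steps near the boundary.
4. Query: reconcile the Protocol 1.3 footnotes, Protocol 7.3, SAP 5.1.3 and the two statements in SAP 6.2, and say how non-responders are classified at the Primary Analysis and in the rerun. Any new definition of missing needs a tolerance. An infant enrolled before 01 September 2022 has its last monthly contact (D181) before the 28 February 2023 cut-off, and should not count as missing when all scheduled contacts are complete.

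The cost is one redrawn graph and its two counterparts, using rows already planned, plus a clarifying sentence; no new data are needed. SAP section 7 records that the Primary Analysis has already been run and rerun, so the change should be labelled as made after those analyses. The displayed robustness may look less favourable in some rows and more favourable in others.

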6.6.3. Supplementary Analyses for the Primary Objective

6.6.3.1. Analyses with Per-Protocol Analysis Set

The above-described analysis in Section 6.6.1 on the primary endpoint will also be conducted on the PPAS.

6.6.3.2. Survival Analyses

A hazard ratio and the corresponding 2-sided 95% CI will be obtained from the Cox proportional hazard model with country (ie, France, Germany and United Kingdom) and age group at randomization (ie, age \leq 3.0 months, age $>$ 3.0 to \leq 6.0 months, age $>$ 6.0 months) as the covariates. The corresponding efficacy estimate is defined as $(1 \text{ minus hazard ratio}) \times 100\%$. A Kaplan-Meier curve for time to first RSV LRTI hospitalization will be generated based on the observed events and will include the p-value from a log-rank test stratified by country and age group at randomization. The algorithm for time-to-event calculation is the same as that for follow-up time as Section 6.6.1.

A log log plot to check Proportional Hazard assumption in the Cox proportional hazard model above will be provided.

Above analyses will be performed in the All Randomized Set.

6.6.4. Secondary Efficacy Analysis

6.6.4.1. Very Severe RSV LRTI

If the efficacy of nirsevimab in preventing RSV LRTI hospitalization is demonstrated in the primary efficacy analysis, the very severe RSV LRTI through the RSV season will be compared between the nirsevimab and no intervention groups on All Randomized Set using the same method as for the primary efficacy analysis of the primary endpoint. The very severe RSV LRTI is a subset of RSV LRTI hospitalization with oxygen saturation $<$ 90% (at any time during hospitalization) and oxygen supplementation. For participants with multiple very severe RSV LRTI episodes, only the first occurrence will be used in the analysis. If the lower bound of the 2-sided 95% CI for the efficacy is $>$ 0%, the superior efficacy of nirsevimab in preventing very severe RSV LRTI compared to the no intervention group is demonstrated. P-value will also be provided.

The algorithm for follow-up time is the same as that for follow-up time as Section 6.6.1.

6.6.4.2. RSV LRTI Hospitalization in Each Country

If the efficacy of nirsevimab in preventing very severe RSV LRTI compared to the no intervention is concluded, RSV LRTI hospitalization will be evaluated in each of the 3 countries. The same analysis as described above in Section 6.6.1 for the primary endpoint with Bonferroni-Holm procedure based on the adjusted p-values for the multiplicity adjustment will be used to calculate the efficacy on All Randomized Set in each country. The

superior efficacy of nirsevimab in preventing RSV LRTI hospitalization is concluded for the country if the adjusted p-value is < 0.05 . The p-values will be ordered from the smallest to the greatest for the 3 countries and give rank 1, to the smallest, and 3, to the greatest. Compare the first-ranked (smallest) p-value to the alpha level $0.05/(3+1 - \text{rank})$. If the p-value is smaller, reject the null hypothesis for this individual test and move to the p-value of the next rank. Otherwise, the hypothesis is not significant and stops the procedure. The testing stops with the first non-rejected null hypothesis. All subsequent hypotheses are non-significant. Only countries with adjusted p-values and the first country with non-significant adjusted p-value will be presented. Adjusted p-values will be computed using PROC MULTTEST in SAS.

At the time of First Year Analysis, the adjusted 2-sided 95% CI for the efficacy will also be calculated by an exact method assuming a binomial distribution of the number of RSV LRTI hospitalizations in the nirsevimab group conditional on the total number in both groups (described by Breslow and Day) accounting for the follow-up time post-dosing/randomization.

The algorithm for follow-up time is the same as that for follow-up time in Section 6.6.1.

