2.3.4 Overall Benefit-Risk Conclusion

Based on the favorable efficacy and safety profiles from the previous studies of nirsevimab in infants entering their first RSV season, nirsevimab offers the ability to provide protection against RSV lower respiratory tract disease.

For participants randomly assigned to receive nirsevimab, considering the measures taken to minimize risk to enrolled participants, the potential risks that may result from study participation are balanced by the anticipated benefits that may be afforded to participants.

For participants randomly assigned to the no intervention group, there are no unreasonable and significant risks of illness or injury foreseen.

All participants will receive the standard of care and routine health care. This includes being informed on current recommendations on RSV prevention through hygiene measures.

3 Objectives and Endpoints

The study objectives and the corresponding endpoints are described in Table 3.1.

Table 3.1: Objectives and endpoints

Objectives	Endpoints
Primary	
To assess the efficacy of nirsevimab in preventing RSV LRTI hospitalization compared to no intervention	Overall incidence of RSV LRTI hospitalization through the RSV season
Secondary	
To assess the efficacy of nirsevimab in preventing very severe RSV LRTI compared to no intervention	• Incidence of very severe RSV LRTI defined as RSV LRTI hospitalization with oxygen saturation < 90% (at any time during hospitalization) and oxygen supplementation, through the RSV season
To assess the efficacy of nirsevimab in preventing RSV LRTI hospitalization compared to no intervention in each country	Incidence of RSV LRTI hospitalization through the RSV season in each country
To assess the efficacy of nirsevimab in preventing hospitalizations for all-cause LRTI compared to no intervention	Incidence of hospitalizations for all-cause LRTI through the RSV season
To assess the efficacy of nirsevimab in preventing RSV LRTI hospitalization through 150 days post-dosing/randomization (overall and in each country)	Incidence of RSV LRTI hospitalization through 150 days post-dosing/randomization (overall and in each country)
To assess the efficacy of nirsevimab in preventing very severe RSV LRTI through 150 days post-dosing/randomization	Incidence of very severe RSV LRTI defined as RSV LRTI hospitalization with oxygen saturation < 90% (at any time during hospitalization) and oxygen supplementation, through 150 days post-dosing/randomization

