2.3. Sample Size and Power

A total of 28,860 participants are expected to be enrolled of whom approximately 14,430 will receive nirsevimab and 14,430 will receive no intervention. This sample size is driven by the demonstration of efficacy in preventing RSV LRTI hospitalization through RSV season in each of 3 countries independently.

Based on the reported incidence rates of RSV LRTI hospitalization in France, Germany, and the United Kingdom ^{1,2,3}, assuming a 1.1% incidence rate on average in the no intervention group, 9,620 participants need to be enrolled in each of the 3 countries (which is equivalent to 74 events of RSV LRTI in each country) to ensure the 90% power to detect 60% efficacy (see definition of efficacy of nirsevimab in preventing RSV LRTI hospitalization compared to no intervention in Section 2.4) in each country with a 2-sided α of 1.66% taking the multiplicity adjustment using Bonferroni approach into consideration.

The sample size of 28,860 participants has at least 99% power to detect 60% efficacy in preventing RSV LRTI hospitalizations in all 3 countries combined assuming an incidence rate of 0.86% in the no intervention group (the lowest reported in the 3 countries ^{1,2,3}) with a 2-sided α of 5%, and approximately 95% power to detect 60% efficacy in preventing very severe RSV LRTI defined in the protocol assuming an incidence rate of 0.4% in the no intervention

group with a 2-sided α of 5%. To ensure at least 90% power for very severe RSV LRTI, at least 61 events are needed.

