6.1. General Principles

All data processing, summarization and analyses will be performed using Fortrea's SAS Environment / Version 9.4 (or later) of the SAS® statistical software package.

The default summary statistics for quantitative variables will be the number of observations (n), mean, standard deviation (SD), median, minimum (min) and maximum (max), for those participants with data.

For qualitative variables, the number (n) and percentage (%) of participants with non-missing data per category will be the default summary presentation, and where appropriate and present, the number of missing values as a "Missing" category. Number of participants in the analysis population will be used as denominator for percentages calculation, unless otherwise stated in TFLs mock shell(s).

All statistical comparisons will be made using two sided tests at the $\alpha=0.05$ significance level unless specifically otherwise stated. All null hypotheses will be of no treatment difference. All alternative hypotheses will be two-sided.

Specifications for table, figure and data listing formats can be found in the TFL shells specifications for this study. Please refer to "2. General Format Guidelines" section within TFL shells for more details on presentation of results.

All analyses in the SAP will be carried out for all countries combined and as subgroup analyses by country.

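### The SAP withholds the through-season RSV LRTI hospitalization efficacy result for any country ranked after the first Holm non-rejection, which Holm does not require

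*SAP*

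**What the plan says.** RSV LRTI hospitalization by country is a key secondary endpoint in the protocol synopsis. Protocol Section 3 (Table 3.1) lists it as "Incidence of RSV LRTI hospitalization through the RSV season in each country", and both documents say the sample size is driven by showing efficacy in each country independently.

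SAP 6.6.4.2 orders the three country p-values and compares them with 0.05/3, 0.05/2 and 0.05 in turn. Its stopping rule is "The testing stops with the first non-rejected null hypothesis. All subsequent hypotheses are non-significant". It then adds a display rule: "Only countries with adjusted p-values and the first country with non-significant adjusted p-value will be presented".

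The display rule recurs in SAP 6.6.5.2.1 (Poisson), 6.6.6.2.1 (per-protocol set) and 6.6.6.2.2 (survival). SAP 6.6.5.2.2 (tipping point) shows only the countries retained under 6.6.4.2. Copies also stand in 6.6.6.1.1 and 6.6.6.1.2, which concern very severe RSV LRTI in all countries combined.

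Other text has no such limit. Protocol 9.4.3.2 evaluates the endpoint in all three countries. SAP 3.3.5 has efficacy and its CI quantified within each country and the adjusted interval presented. SAP 6.1 states: "All analyses in the SAP will be carried out for all countries combined and as subgroup analyses by country".

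**The concern.** Whether a country's result is reported depends on the result. If the smallest p-value fails, two of three countries are left out; if the second fails, one is. Those left out have the largest p-values, so the countries that remain look more favourable and more alike than the full set.

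Holm controls the chance of a false superiority claim. Once it stops, no further claim may be made, but an estimate with its interval, labelled as not tested, is not a claim and spends no alpha. What is at stake is a reader's ability to judge consistency across countries on the endpoint that set the sample size.

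**Working it through.** **Inputs.** From SAP 2.3: 9,620 participants and 74 events per country; control incidence 1.1%; 60% efficacy (rate ratio 0.40); 90% power; two-sided α 1.66%; very severe incidence 0.4% in controls. From SAP 6.7.8: the Primary Analysis runs once at least 61 events are seen in all countries combined, and no later than 30 April 2023. Allocation is 1:1. Assumptions: equal true efficacy in all countries, equal person-time by arm, and the event splits stated below.

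**Step 1: reproduce the plan's figure.** The nirsevimab rate is 0.4 × 1.1% = 0.44%. Expected events are 4,810 × (0.011 + 0.0044) = 74.1, matching 74. The two-proportion formula at α = 0.0166 and 90% power gives 4,741 per arm, or 9,482 per country, 1.4% below 9,620. The sizing is sound and is not in dispute.

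**Step 2: when a country is withheld.** Order p(1) ≤ p(2) ≤ p(3).
- p(1) > 0.0167: two countries withheld.
- p(1) ≤ 0.0167 and p(2) > 0.025: one withheld.
- Otherwise none; if only the third fails, it is still shown as the first non-significant country.

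**Step 3: hand check at 74 events each, 60% efficacy.** Given 74 events, the nirsevimab count is binomial with probability 0.4/1.4 = 0.286, tested against 0.5. A count of 26 or fewer meets both the 0.0167 and the 0.025 thresholds, and 27 meets neither. Per-country power is 91.4%, so the failure probability is 0.086. A country is withheld when two or more fail: 3 × 0.086² × 0.914 + 0.086³ = 0.0203 + 0.0006 ≈ 2.1%.

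**Step 4: simulation.** 200,000 trials per scenario, exact two-sided conditional binomial p-values, Holm as in SAP 6.6.4.2. Ranges span fixed and Poisson event counts and, at 61 events, a near-equal and a 30/16/15 split.

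| Events | True efficacy | At least one country withheld |
|---|---|---|
| 74 each | 60% | about 2% |
| 74 each | 40% | 62–67% |
| 61 in total | 60% | about 78–82% |

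These figures take the country step as reached. SAP 6.6.4.2 reaches it only after both the primary and the very severe tests succeed. Taking the very severe share of events as 0.4/1.1, both succeed in about 44% of trials at 61 events and 60% efficacy. Among those trials, about 64–69% withhold at least one country.

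**Step 5: selection.** With 61 events split 50/25/25 (the protocol gives the UK half of the study population; the rest is assumed) and 60% true efficacy everywhere, median estimated efficacy is about 69% in the countries shown and 44% in those withheld.

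**The case against.** The strongest reply has four parts.

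1. **The sentence is loosely worded.** Read literally, all three countries have an adjusted p-value, so nothing would be dropped, and the copies in the very severe sections suggest pasted text. The pasting is plausible, but the literal reading fails: the added phrase about the first non-significant country has no purpose unless later ones are left out.

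2. **Country data appear elsewhere without a Holm gate.** This stands. The SAP gives RSV LRTI hospitalization efficacy by country through Day 151 and Day 181 (6.6.4.3.2, 6.6.4.3.4), season all-cause LRTI efficacy by country (6.6.4.3.1), season very severe RSV LRTI by country (6.6.8.2), and season utilization counts by country and arm (6.6.7.4). A reader might infer that a country's data vanish altogether, and the documents do not support that. But these are other endpoints, other windows or counts, and the Day 151 and Day 181 results come only at the First Year Analysis. Country is not among the primary-endpoint subgroups in 6.6.8.1. The by-country sentence in 6.1 is general and does not clearly override a specific, repeated rule.

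3. **Holm ranks by p-value, not by effect.** This also stands. A reader might infer that the weakest country is always the one lost. A country with few events can be withheld with a better estimate: under a fixed 30/16/15 split, the last-ranked country was not the lowest estimate in about 14% of trials that withheld one.

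4. **The large percentages are not typical.** The 61-event trigger is a minimum, and the chance is about 2% at the planned event count. If the very severe test fails, the country step is never reached and this sentence is not the cause.

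**Conclusion.** The point holds in a bounded form. For any country ranked after the first Holm non-rejection, the SAP withholds the through-season RSV LRTI hospitalization efficacy estimate, CI and p-value. This is results-dependent reporting of a key secondary endpoint. The multiple-testing procedure does not need it, and the passages in the protocol and SAP that call for results in each country contradict it. The countries affected have the largest p-values, usually but not always the lowest estimates.

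The size depends on events and efficacy. The rule is almost harmless at the design point and bites when either falls short, which is when a reader most needs all three results. The percentages rest on equal efficacy across countries and, at 61 events, on assumed country splits. The conditional figure also assumes a very severe share of 0.4/1.1. The documents do not support reading the rule as deliberate concealment or as hiding all data for a country.

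**What to change.** Delete the display sentence in SAP 6.6.4.2, 6.6.5.2.1, 6.6.6.2.1 and 6.6.6.2.2, and remove the matching limit in 6.6.5.2.2. Remove the misplaced copies in 6.6.6.1.1 and 6.6.6.1.2, where the endpoint is not by country.

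State instead that events, person-time, efficacy and CI are presented for all three countries, with any rank after the first Holm failure marked 'not tested; descriptive'. Keep the Holm stopping rule as it is.

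The cost is a SAP wording change and a few more table rows. Alpha, sample size and power are unchanged.
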